### 7.3. Average daily wear time (in Hours)

Average daily wear time will be calculated as the number of hours between subjects reported time of insertion and time of removal of the study lenses at screening 3-Day Follow-up and 2-Week Follow-up evaluation.

### 7.4. Definition of Subgroups

Subject will be categorized into either the Hyperope or the Myope group based on the subjects' distance spherical refraction. Subjects who have a negative distance spherical refraction will be categorized as a Myope while subjects who have a positive distance spherical refraction will be categorized as a Hyperope. However, if a subject has positive distance spherical refraction in one eye and plano refraction in the opposite eye then the subject will be categorized as a Hyperope. If the subject has negative distance spherical refraction in one eye and plano refraction in the opposite eye, then the subject will be categorized as a Myope. If the subject has positive distance spherical refraction in one eye and negative distance spherical refraction in the other eye, the eye with the highest absolute power (D) will be used to categorize the subject (i.e. if a subject spherical distance refraction is OD: +0.75, OS: -1.25; then they will be categorized as a Myope. If the subject has equal magnitude of spherical refraction but opposite sign between eyes, the subject will be categorized as a Myope.

## **8. GENERAL STATISTICAL CONSIDERATIONS**

### **8.1. Statistical Software**

All data summaries and statistical analyses will be performed using the SAS software Version 9.4 or higher (SAS Institute, Cary, NC).

### **8.2. Summary Statistics**

Throughout the analysis of data, the results for each subject/eye will be used when available for summarization and statistical analysis. Unscheduled visits will be summarized separately and will be excluded from the efficacy statistical analysis but will be included in the analysis of safety endpoints (slit lamp findings and lens fitting).

Summary tables (descriptive statistics and/or frequency tables) will be provided for all baseline variables, efficacy variables and safety variables as appropriate. Continuous variables will be summarized with descriptive statistics (n, mean, standard deviation [SD], median, minimum, and maximum). Frequency count and percentage of subjects or eyes within each category will be provided for categorical data.

Safety and efficacy variables will be summarized on both safety and PP populations.

### **8.3. Reporting Numerical Values**

Means, medians and confidence/credible intervals will be reported to one decimal place greater than the original data. The standard deviation will be reported to two decimal places greater than the original data. Minimum and maximum will use the same number of decimal places as the original data. P-values greater or equal than 0.0001 will be reported to 4 decimal places; p-values less than 0.0001 will be reported as “<0.0001”. All percentages will be reported to one decimal place.

### **8.4. Sample Size Justification**

This study was designed and powered to demonstrate that the Multifocal Test lens made with senofilcon A material made from the Flexible Manufacturing Platform (FMP), in its final lens design FAL100, FAL101 and FAL102 (low, mid and high ADD respectively) meets the design validation requirements for the following efficacy and safety endpoints:

- CLUE vision score at 2-week follow-up
- Binocular visual acuity (Distance, Intermediate and Near) at 2-week follow-up
- Proportion of eyes with a significant slit lamp finding (Grade 3 or higher)
- Proportion of eyes with unacceptable lens fitting

The historical data used for the sample size calculation were from 6 JJVC sponsored studies. Table 4 displays the studies, their corresponding study design and the number of subjects enrolled and

**CR-6400, Statistical Analysis Plan Version 1.0**

completed. The investigational product in all these studies was the multifocal Test lens in its' final design (FAL100, FAL101 and FAL102) made from different manufacturing platforms.

Table 4: Historical Studies Utilized for Sample Size Calculation

Study	Study Design	Manufacturing Platform	#Enrolled	#Completed	Population	SKU
█	Crossover	FMP 	46	43	Hyperopes	+1.00 to +4.00
█	Crossover	TAM21 	71	61	Hyperopes	+1.00 to +4.00
█	Crossover	TAM21	63	60	Myopes	-1.00 to -4.00
█	Crossover	SCLM 	45	45	Hyperopes	+1.00 to +4.00
█	Parallel	MCLM 	189	168	Myopes	-1.00 to -4.00
█	Crossover	SCLM	40	34	Hyperopes	+1.00 to +4.00
Total			454	411		

FMP: Flexible Manufacturing Platform

TAM21: Tokyo Automatic Machinery -3GT (3rd Generation Technology) manufacturing line

SCLM: Single Cavity Lens Machine

MCLM: Multi Cavity Lens Machine

Summaries of efficacy data pooled across all the 6 studies are presented in Table 5. Results showed that near, intermediate and distance VA have similar variation across studies, therefore a 0.11 was utilized for the variation in the power calculation for all positions. Historical data have shown that the average CLUE vision score of hyperopes is lower that of myopes.

Table 5: Descriptive summary of Efficacy Endpoints Period 1 Only - 2-Week Follow-up

Endpoint	Mean	Median	Standard Deviation	Minimum	Maximum
Distance VA (3m)	-0.077	-0.100	0.1026	-0.320	0.560
Intermediate VA (64cm)	-0.054	-0.060	0.1014	-0.300	0.360
Near VAR (40cm)	0.077	0.060	0.1100	-0.260	0.460
Hyperopes' CLUE Vision score	47.71	48.07	17.514	10.22	93.50
Myopes' CLUE Vision score	56.46	53.37	19.227	21.51	108.04

The proportion of eyes with Grade 3 or higher SLFs and the proportion of eyes with unacceptable lens fittings pooled across all historical studies is presented in the table below. As shown, there was only 1 unacceptable lens fitting in any of the 6 historical study while there have been 5 eyes with reported Grade 3 or higher SLFs.

Table 6: Descriptive Summary of Safety Endpoints all available Data

Endpoint	Test n(%)
Unacceptable lens fitting	1 (0.2)
SLF Grade 3+	5 (1.4)
Total Eyes (N)	350
Total Subjects	175

%= nx100/N

### **Safety Analysis**

Our plan for safety analysis is to incorporate historical individual subject data from the 6 studies using power prior distributions in a Bayesian framework (see section 14.5). The level of influence of historical data on current is determined by a discounting factor  $a_0$  constrained between 0 and 1 ( $0 \leq a_0 \leq 1$ ).  $a_0 = 0$  corresponds to no borrowing of the historical data; while  $a_0 = 1$  corresponds to full borrowing (See section 14.5 for more details). For this study we considered a low level of borrowing ranging by 0.1 and 0.30 based on the manufacturing platform where the historical study lens was made from. Table 7 displays the number of subjects and the degrees of borrowing that will be used in the safety analysis. The approved investigational product will be manufactured from the FMP platform; therefore, the borrowing strength is larger to lenses from the FMP platform. Furthermore, the TAM21 platform is considered equivalent with respect to lens performance and lenses from these platforms are given the same borrowing strength as those from the FMP platform. While all historical studies used the lens in its final design, lenses made from the pilot line are only given a borrowing strength of 10%.

Table 7: Degrees of Borrowing Historical Data by Manufacturing Platform

Manufacturing Platform	Number of Subjects	Level of borrowing ( $a_0$ )
FMP	23	0.3
TAM21	66	0.3
Pilot Line (SCLM, MCLM)	86	0.1

We calculated the required sample size with and without borrowing historical data. To achieve a minimum of 80% power with a 2-sided type I error rate of 5%, the required sample size with no borrowing ( $a_0 = 0$ ) was 120 subjects (240 eyes); while the sample size with borrowing was 60 subjects (120 eyes). The sample calculation in each scenario of borrowing was conducted using a Monte Carlo simulation of 1000 trials of samples of size 120 subjects (240 eyes) were drawn from a multivariate binary distribution assuming a compound symmetric (CS) covariance structure between left and right eye from the same subject. Assuming a true proportion of eyes with grade 3 or higher SLFs of  $p=0.014$  and a correlation of  $\rho=0.70$  between left and right eyes. The same approach was considered for the proportion of eyes with unacceptable fitting assuming a true proportion of eyes with unacceptable fit of  $p=0.01$  and a correlation of  $\rho=0.80$  between left and right eyes.

The sample size was mainly driven by safety analysis, the power calculation of the efficacy analysis showed that a sample size of 60 subjects is sufficiently large to test the efficacy hypotheses. No borrowing was considered for the primary efficacy analysis. Table 8 summarize the statistical power of a sample size of 60 subjects (120 eyes) for all endpoints.

Table 8: Power calculation by endpoint/hypothesis assuming a sample size of 60 subjects

Endpoint	Borrowing	Hypothesis ( $H_A$ )	Power (%)
Grade 3 or Higher SLFs	Yes	$p_t < 0.05$	80
Unacceptable lens tit	Yes	$p_t < 0.05$	90
VA Distance	No	$\mu_t < +0.10$	> 99
VA Intermediate	No	$\mu_t < +0.17$	> 99
VA Near	No	$\mu_t < +0.17$	> 99
CLUE Vision (Hyperopes)	No	$\mu_t \geq 32$	99
CLUE Vision (Myopes)	No	$\mu_t \geq 40$	99

The power calculation of the efficacy analyses (CLUE and VA) was conducted using historical data presented in Table 5 above using PROC POWER for one sample means test for equivalence to test each hypothesis.

The plan is to enroll 80 eligible subjects with a target completion of 60 subjects. During the enrollment period, the subject drop-out rate will be closely monitored, if an unexpectedly high dropout rate is observed, then the targeted total enrollment number maybe be increased accordingly to ensure that a minimum of 60 subjects complete the study.

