## 8.5. Statistical Significance Level

All planned analysis for this study will be conducted with an overall type I error rate of 5%.

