#### **Primary Safety Analyses:**

Slit lamp finding grade 3 or higher and unacceptable lens fitting responses (yes/no) will be analyzed separately on the safety population using the Bayesian model described below. A sensitivity analysis will be conducted with no borrowing of historical data.

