## Hypothesis Testing

With respect to unacceptable lens fit the null and alternative hypothesis for superiority is as follows:

$$\begin{aligned} H_o &: p_T \geq 0.05 \\ H_A &: p_T < 0.05 \end{aligned}$$

Where,  $p_T$  represents the proportion of subject eyes that are considered to have unacceptable fit for the study lens after 2-weeks of lens wear. Success for unacceptable fit will be declared if the upper bound of the 2-sided 95% credible interval of the proportion is lower than 0.05; i.e.  $P(p_T < 0.05) \geq .975$ .

With respect to Grade 3 or Higher SLFs the null and alternative hypothesis for superiority is as follows:

$$H_o : p_T \geq 0.05$$

$$H_A : p_T < 0.05$$

Where,  $p_T$  represents the proportion of subject that experienced any Grade 3 or Higher SLF or experienced a corneal infiltrate. Success for Grade 3 or higher SLFs will be declared if the upper bound of the 2-sided 95% credible interval of the proportion is lower than 0.05; i.e.  $P(p_T < 0.05) \geq .975$ .

If no SLF findings of Grade 3 or higher or unacceptable lens fit is observed, alternative analysis methods may be considered.

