### SLF (Grade 3 or Higher) and Unacceptable Lens Fitting

- With Borrowing

```
PROC MCMC DATA= ADS DIC =brief
NBI=50000 NMC=80000 THIN=15 STATS=ALL MONITOR=( parms_ ) STATS(ALPHA=(0.05)
PERCENTAGE=(2.5 25 50 75 97.5) ) SEED=14789652 ;
PARM p ro .5 ;
PRIOR ro ~ UNIFORM(0,1);
PRIOR p ~ BETA(0.5, 0.5);
BEGINCNST;
IF studyid in [REDACTED] ) THEN a0 = 0.3;
ELSE IF studyid in ( [REDACTED] THEN a0 = 0.3;
ELSE IF studyid in [REDACTED] ) THEN a0=0.1;
ENDCNST;
llike = log( (1-ro)*PDF('BINOMIAL', y, p, 2) + z*ro*(p**y*(1-p)**(2-y))***(1/2) );
IF studyid in ( [REDACTED] ) THEN llike = llike; ELSE llike = a0*llike;
MODEL y ~ GENERAL(llike);
RUN;
```

- Without Borrowing

```
PROC MCMC DATA= ADS DIC =brief
NBI=50000 NMC=80000 THIN=15 STATS=ALL MONITOR=( parms_ ) STATS(ALPHA=(0.05)
PERCENTAGE=(2.5 25 50 75 97.5) ) SEED=14256983 ;
PARM p ro .5 ;
PRIOR ro ~ UNIFORM(0,1);
PRIOR p ~ BETA(0.5, 0.5);
BEGINCNST;
IF studyid in [REDACTED] ) THEN a0 = 0;
ELSE IF studyid in ( [REDACTED] ) THEN a0 = 0;
ELSE IF studyid in [REDACTED] ) THEN a0=0;
ENDCNST;
llike = log( (1-ro)*PDF('BINOMIAL', y, p, 2) + z*ro*(p**y*(1-p)**(2-y))***(1/2) );
IF studyid in ( [REDACTED] ) THEN llike = llike; ELSE llike = a0*llike;
MODEL y ~ GENERAL(llike);
RUN;
```

Where,

ads = Analysis dataset for Grade 3 or higher SLFs or Unacceptable Lens Fitting

a0 = degree of borrowing

studyid=Study Identifier

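### The stated safety power (80% and 90% at 60 subjects with borrowing) and the 5% type I error do not follow from the SAP's own decision rule, and the simulation is described at 120 subjects

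*SAP*

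**What the plan says.** SAP 8.4, under Safety Analysis, states: "To achieve a minimum of 80% power with a 2-sided type I error rate of 5%, the required sample size with no borrowing" was 120 subjects (240 eyes), and 60 subjects (120 eyes) with borrowing. It describes the method for each borrowing scenario as a "Monte Carlo simulation of 1000 trials of samples of size 120 subjects (240 eyes"). The design values are p = 0.014 with between-eye correlation 0.70 for SLF, and p = 0.01 with correlation 0.80 for fit. It continues: "Table 8 summarize the statistical power of a sample size of 60 subjects (120 eyes) for all endpoints". That table lists 80% for SLF and 90% for fit, both with borrowing. Protocol 14.2 carries the same text and figures.

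On error, SAP 8.5 (as protocol 14.4) says: "All planned analysis for this study will be conducted with an overall type I error rate of 5" percent. On the rule, SAP 11.1 says: "Success for unacceptable fit will be declared if the upper bound of the 2-sided 95% credible interval of the proportion is lower than 0.05", which it equates to a posterior probability of at least .975. The SLF rule is the same. SAP 11.1 also plans: "A sensitivity analysis will be conducted with no borrowing of historical data". The analysis code in SAP 14.2.1 sets "PRIOR p ~ BETA(0.5, 0.5") for the proportion, a uniform(0,1) prior for the correlation, and "NBI=50000 NMC=80000 THIN=15" for the sampler.

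**The concern.** SAP 8.4 says the safety endpoints drove the sample size, so the 80% and 90% entries are the justification for 60 subjects. Borrowing is what halves N from 120 to 60. If the rule in SAP 11.1 does not give those powers at 60, the halving is unsupported.

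Borrowing from a favourable history also raises the chance that a lens sitting on the 5% limit passes. Neither document reports a type I error for the borrowing rule, yet both claim 5%. Finally, simulating 120 subjects in every scenario cannot by itself yield a power table for 60.

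**Working it through.** **Inputs.**
- Prior: Beta(0.5, 0.5) for p and uniform(0,1) for ρ (SAP 14.2.1).
- Borrowing (SAP Table 7): a0 = 0.3 for 23 + 66 = 89 FMP and TAM21 subjects, a0 = 0.1 for 86 pilot-line subjects. Effective history = 0.3×89 + 0.1×86 = 35.3 subjects.
- Historical events (SAP Table 6): 5 SLF eyes and 1 unacceptable-fit eye among 350 eyes (175 subjects).
- Assumption: the documents do not give the platform or the eye pairing of these events, so I ran a range.

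**Model (SAP 11.1).** Per subject:
- P(no eye) = (1−ρ)(1−p)² + ρ(1−p)
- P(one eye) = 2(1−ρ)p(1−p)
- P(both eyes) = (1−ρ)p² + ρp

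I integrated the posterior numerically for each outcome (number of one-eye subjects, number of two-eye subjects). An outcome passes if P(p<0.05) ≥ .975. I then summed exact trinomial probabilities over the passing outcomes.

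**Power: the plan's figures do not reproduce.**

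| Setting | Passing outcomes | Power | Plan |
|---|---|---|---|
| SLF, N=60, borrowing, all five eyes pilot line | (0,0), (1,0), (2,0), (0,1) | 74.5% | 80% |
| SLF, N=60, borrowing, all five eyes FMP/TAM21 | (0,0), (1,0) | 50.2% | 80% |
| Fit, N=60, borrowing, event on either platform | (0,0), (1,0), (2,0), (0,1) | 85.2% | 90% |
| SLF, N=120, no borrowing | (0,0) to (4,0), (0,1) to (2,1), (0,2) | 71.9% | at least 80% |

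The SLF rows at N=60 can be checked by hand. With p = 0.014 and ρ = 0.70:
- P(no eye) = 0.3×0.986² + 0.7×0.986 = 0.98186
- P(one eye) = 2×0.3×0.014×0.986 = 0.00828
- P(both eyes) = 0.3×0.014² + 0.7×0.014 = 0.00986
- (0,0): 0.98186⁶⁰ = 0.333
- (1,0): 60×0.98186⁵⁹×0.00828 = 0.169
- (0,1): 60×0.98186⁵⁹×0.00986 = 0.201
- (2,0): 1770×0.98186⁵⁸×0.00828² = 0.042

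The first two sum to 0.502 and all four to 0.745. Mixed platform splits with an exact posterior give one or other of these values.

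The simulation error of 1000 trials is √(0.8×0.2/1000) = 1.3 points at 80% and √(0.9×0.1/1000) = 0.9 at 90%. The smallest gaps are 80 − 74.5 = 5.5 and 90 − 85.2 = 4.8 points.

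**Sampler noise.** The code keeps 80000/15 = 5,333 draws, so the standard error at .975 is at least √(0.975×0.025/5333) = 0.0021. Some outcomes lie that close to the threshold:
- Fit, event on the pilot line: (1,1) has posterior 0.9739 and (3,0) has 0.9743. If both pass, fit power is 90.9% and the false-pass rate about 22% at ρ of 0.7 to 0.8. Averaged over the noise, power is 86.9% and the false-pass rate at ρ = 0.8 is 16.5%.
- Fit, event on FMP/TAM21: both are at 0.969 and clearly fail.
- SLF, for example three FMP/TAM21 and two pilot eyes: (2,0) and (0,1) are at about 0.974, giving 58–59% power under the noise.

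**False-pass rate at p = 0.05, N=60, history fixed.**

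| Test | ρ=0 | ρ=0.5 | ρ=0.7 | ρ=0.8 |
|---|---|---|---|---|
| Fit, borrowing | 5.8% | 10.5% | 12.6% | 13.9% |
| SLF, borrowing, events pilot line | 5.8% | 10.5% | 12.6% | 13.9% |
| SLF, borrowing, events FMP/TAM21 | 1.6% | 4.1% | 5.3% | 5.6% |
| Either, no borrowing | 1.6% | 4.1% | 5.3% | 5.6% |

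The last row is a near tie. Outcome (1,0) passes with posterior 0.97506. If it failed, the rates would be 0.2% (ρ=0), 1.0% (0.5) and 2.5% (0.8).

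**N simulated.** At 120 subjects with borrowing, SLF power is 82.1–89.8% and fit power 96.0%. The 80% target is therefore met at the size the text describes, not at the size in the table.

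**What does come near 80/90.** A looser threshold of P ≥ .95 at N=60 with borrowing gives SLF 74.5–85.2% and fit 90.9%, with a fit false-pass rate of 22.4%. The SAP states .975.

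**The case against.** **The prior used for the power simulation is not stated.** The sample-size text names none, and the methods text has only a generic beta(α, β). Beta(0.5, 0.5) appears only in the SAP code, which postdates the protocol's power figures. With Beta(0.1, 0.1), an assumption, the .975 rule gives 82.1% for SLF at 120 without borrowing and 90.9% for fit at 60. This stands as a possible origin of the figures. It does not rescue them. SLF at 60 exceeds 80% only if all five events are pilot line (85.2%), and is 74.5% for the other splits tried. The fit false-pass rate then becomes 14–22%. The planned analysis uses the coded prior, so its operating characteristics are the relevant ones.

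**The safety population may exceed 60.** It includes everyone given a lens, and 80 are to be enrolled. At 80, SLF power is still 62.5–76.0%. Fit power is 86–94%, so the fit shortfall is the less robust part, but the fit false-pass rate is then 9.4–17.7%.

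**Error conditional on a favourable history is built into borrowing.** If the history is redrawn at p = 0.05, the SLF error is about 1.3%. But the historical data are already observed, so the fixed-history rate is the one this trial faces. Redrawing the history at the design rate still leaves SLF power at about 64%.

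**All seven hypotheses must pass.** This is true, and it makes the single-test rate a ceiling for the trial. With fit at p = 0.05, SLF at its design rate and independence assumed, both pass between 0.139×0.502 = 7.0% and 0.139×0.745 = 10.4% of the time at fit ρ = 0.8. At ρ = 0 the range is 0.058×0.502 = 2.9% to 0.058×0.745 = 4.3%.

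**The 120-subject wording may be a drafting slip.** It may be, but as written the text contradicts the table. Low power is also mainly the sponsor's risk, which is why the fix leaves N alone.

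**Conclusion.** The concern holds. Under the SAP's model, coded prior, borrowing weights and .975 rule:
- SLF power at 60 is 5.5 to 29.8 points below the stated 80%.
- Fit power is about 5 points below the stated 90%.
- The no-borrowing SLF power at 120 is about 8 points below the stated minimum. This figure does not depend on the historical events.
- The borrowing-based fit test exceeds 5% false passes at every correlation from 0 to 0.8. For SLF it depends on the correlation and on the undisclosed platform of the five eyes.

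The SLF shortfall and the fit false-pass excess are the firmest results. The fit power gap is sensitive to sampler noise and to how many subjects enter the safety population. All borrowing figures rest on the coded prior and on the range assumed for the platform and pairing of the historical events.

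**What to change.** - Re-run the simulation at 60 subjects with the .975 rule, the coded prior and the actual platform and laterality of the historical events. State the prior and the N simulated in each borrowing scenario.
- In SAP 8.4 and protocol 14.2, replace the 80% and 90% entries and the 80%-at-120 claim with the values obtained, and justify 60 subjects against them.
- Report the simulated false-pass rate at p = 0.05 over a range of ρ for hypotheses 6 and 7, with and without borrowing. Note where an outcome sits on the threshold.
- In SAP 8.5 and protocol 14.4, stop claiming 5% type I error for the borrowing-based safety tests.
- Present the already planned no-borrowing result beside the primary one.

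N stays at 60 and the decision rule is unchanged. The cost is one re-run of an existing simulation and wording changes in both documents. The stated figures will look less favourable.

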## 8.5. Statistical Significance Level

All planned analysis for this study will be conducted with an overall type I error rate of 5%.

## 8.6. Handling of Missing Data and Drop-outs

Missing or spurious values will not be imputed. The count of missing values will be included in the summary tables and listings.

Subject dropout is expected to be one of the main reasons of missing data in this clinical trial. Past clinical trials don't provide the evidence that subject dropout is systematic or not-at-random. To evaluate the impact of missing data, sensitivity analysis will be conducted using fully Bayesian imputation by imputing missing values.

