3.11	Lens Deposits	Grade and record the amount of front and back surface lens deposits for both eyes.	
3.12	Lens Wettability	Grade the wettability of the lenses.	
3.13	Lens Removal	
Have the subject remove the study lenses and store in saline in a labeled glass vial.
 
NOTE: Lenses do not need to be stored in a refrigerator.
	
3.14	Biomicroscopy	Perform Biomicroscopy OD and OS. FDA Slit Lamp Classification Scales* will be used to grade the findings.	

Clinical Study Protocol
Johnson & Johnson Vision Care, Inc.

		
*note: for corneal staining note location (nasal, temporal, superior, inferior or central)
 
If any of these slit lamp findings are Grade 3 or higher, an AE must be recorded. All AEs must be followed to resolution. After resolution the subject will be discontinued and Final evaluation completed
 
If the clearance of the fluorescein needs to be expedited, preservative-free rewetting drops may be instilled.
	
--	--	---	--

FINAL EVALUATION

The final evaluation will ordinarily take place immediately following the last scheduled follow-up visit per the study protocol. It may also take place at any point the subject discontinues the study or is terminated from the study.

Final Evaluation			
Step	Procedure	Details	
F.1	Distance Subjective Sphero-cylindrical Refraction and Distance Exit Visual Acuity	Perform bare-eye subjective sphero-cylindrical refraction with a phoropter and record the best corrected distance visual acuity to the nearest letter (OD, OS, and OU).	
F.2	Subject Disposition	Indicate if the subject completed the study successfully. If subject discontinued from the study indicate the reason.	

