8.2. Withdrawal/Discontinuation from the Study

A subject will be withdrawn from the study for any of the following reasons:

- Subject death during the study period
- Subject withdrawal of consent
- Subject not compliant to protocol
- Subject lost to follow-up
- Subject no longer meets eligibility criteria (e.g. the subject becomes pregnant)
- Subject develops significant or serious adverse events causing discontinuation of study lens wear
- Subjects who have experienced a Corneal Infiltrative Event (CIE)
- Investigator's clinical judgment regarding the subject safety reasons (that it is in the best interest of the subject to stop treatment)
- Subject missed any study visits
- Subject not compliant with study lens wear schedule
- Subject not successfully dispensed due to lack of efficacy and safety including poor vision, poor comfort or unacceptable fit

For discontinued subjects, the Investigator will:

- Complete the current visit (scheduled or unscheduled)
- Complete the Final Evaluation, indicating the reason that the subject was discontinued from the study
- Record the spherocylindrical refraction with best corrected distance visual acuity
- Collect used test article(s) (worn or brought to the visit) from the subject and discard them, unless otherwise stated in Section 7.2
- Collect all unused test article(s) from the subject

An additional subject may be enrolled if a subject discontinues from the study prematurely.

In cases where a subject is lost to follow-up, every possible effort must be made to contact the subject and determine the reason for discontinuation/withdrawal. The measures taken to follow up must be documented including two written attempts and a certified letter (or equivalent) as the final attempt.

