### **6.4. Per-Protocol (PP)**

Per Protocol Analysis set will be the primary analysis population. It will include all subjects who have successfully completed all visits and did not substantially deviate from the protocol as determined by the trial cohort review committee prior to database hard lock. Justification of excluding subjects with protocol deviations in the per-protocol population set will be documented in a memo to file.

The following is a preliminary list of criteria that may disqualify a subject from the Per-Protocol analysis. This list is simply suggestive and is subject to change at the pre-lock review:

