### **Primary Efficacy Analyses**

Efficacy analysis will be conducted the Per-Protocol Population without borrowing from historical data. A sensitivity analysis will be performed by incorporating historical data. The level of borrowing used in the safety analysis will be considered. Further sensitivity analyses on the Safety population may also be considered if the observed subject dropout rate exceeds 15%.

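### The one committed missing-data check is unspecified, assumes missing at random by default, and never lets subjects who left because of the lens be worse than their observed data predict

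*SAP*

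**What the plan says.** SAP section 8.6 (the same text is in protocol section 14.9) has three parts. The main analysis leaves gaps as they are: "Missing or spurious values will not be imputed". The justification is "Past clinical trials don't provide the evidence that subject dropout is systematic or not-at-random". The check is "sensitivity analysis will be conducted using fully Bayesian imputation by imputing missing values". The text does not say which model generates the imputed values, which subjects receive them, or what is assumed about why they are missing. Neither document plans a delta adjustment, a tipping point or any treatment of leavers as failures.

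The SAP's Primary Efficacy Analyses text says "Efficacy analysis will be conducted the Per-Protocol Population without borrowing from historical data", and section 6.4 restricts that set to subjects who "successfully completed all visits and did not substantially deviate from the protocol". Under SAP section 1 the SAP prevails over the protocol, which had named the ITT set. One other check bears on dropout: "Further sensitivity analyses on the Safety population may also be considered if the observed subject dropout rate exceeds 15" per cent.

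The reasons for withdrawal in protocol section 8.2 include "Subject not successfully dispensed due to lack of efficacy and safety including poor vision, poor comfort or unacceptable fit". SAP section 10.1 lists unsatisfactory vision and lens discomfort among the reasons for discontinuation. LogMAR acuity is taken only at Visit 3 (step 3.8). CLUE is taken at Visits 2 and 3, and the SAP models the two scores jointly. For a subject who stops early, Final Evaluation step F.1 reads "Perform bare-eye subjective sphero-cylindrical refraction with a phoropter and record the best corrected" distance acuity, which is not an on-lens measure.

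**The concern.** This is a single-arm test against fixed limits, and all seven co-primary hypotheses must pass. No control arm absorbs selective loss. If subjects who dislike their vision leave and the analysis set is those who stayed, the CLUE and acuity means tend to be flattered.

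A missing-data sensitivity analysis should ask how bad the unseen results would have to be before the conclusion changed. Imputation under missing at random does not ask that. It assumes leavers follow the pattern of completers with the same covariates and earlier scores. Agreement between it and the primary result could then be reported as robustness without the relevant assumption having been tested.

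**Working it through.** **The plan's own figures.** Inputs from SAP section 8.4: CLUE mean and SD 47.71 and 17.514 (hyperopes), 56.46 and 19.227 (myopes); near acuity mean 0.077; acuity SD 0.11; 30 completers per stratum. One-sample t power at one-sided 0.025 is 99.7% for hyperope CLUE, 99.5% for myope CLUE and above 99.9% for each acuity test. This agrees with SAP Table 8 (99, 99 and above 99).

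**Attrition.** From SAP Table 4, (enrolled − completed)/enrolled by study is 3/46 = 6.5%, 10/71 = 14.1%, 3/63 = 4.8%, 0/45 = 0%, 21/189 = 11.1% and 6/40 = 15.0%. Pooled, it is 43/454 = 9.5%. No study exceeded 15%, so at historical loss the optional Safety-population analysis would not be triggered. The plan's own allowance, 80 enrolled for 60 completers, is 25%. That is an upper scenario, because the SAP's total enrolled includes subjects never dispensed.

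**Acuity.** A simulated Visit 3 outcome (60 observed, 20 missing, SD 0.11, covariates known for all) was analysed by one Bayesian model, with and without imputing the missing 20. Both gave 0.063 (95% interval 0.035 to 0.091). A subject with no Visit 3 value adds nothing to the likelihood, and drawing that value from the same model adds nothing either.

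**CLUE.** If leavers with a 3-day score are included, the 2-week mean moves by ρ × gap × m/(n+m). Here ρ is the 3-day to 2-week correlation, gap is the leavers' 3-day deficit, n is completers and m is leavers. Neither ρ nor gap is in the documents. Assuming ρ of 0.5 to 0.8, a gap of 10 to 30 points, n = 30 and m = 10:
- smallest shift: 0.5 × 10 × 10/40 = 1.25, so 47.71 becomes 46.46
- largest shift: 0.8 × 30 × 10/40 = 6.00, so 47.71 becomes 41.71

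**Tipping values.** Let N = n + m and h = t(0.975, N−1) × SD/√N. The test just fails when the overall mean equals limit + h (CLUE) or limit − h (acuity). The missing subjects' mean is then (N × that value − n × completer mean)/m.

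| Case | h | Overall mean needed | Missing subjects' mean at the tip |
|---|---|---|---|
| Hyperope CLUE, 30 at 40, 10 missing | 5.60 | 37.60 | (40×37.60 − 30×40)/10 = 30.4 |
| Hyperope CLUE, 30 at 40, 3 missing | 6.21 | 38.21 | 20.3 |
| Hyperope CLUE, 30 at 47.71, 10 missing | 5.60 | 37.60 | 7.3 |
| Hyperope CLUE, 30 at 47.71, 3 missing | 6.21 | 38.21 | −56.8 (impossible) |
| Near acuity, 60 at 0.13, 20 missing | 0.0245 | 0.1455 | 0.192 |
| Near acuity, 60 at 0.077, 20 missing | 0.0245 | 0.1455 | 0.351 |

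With completers alone, a hyperope mean of 40 passes (40 − 6.54 = 33.5, above 32), and so does a near mean of 0.13 (0.13 + 0.028 = 0.158, below 0.17). Letting the SD widen for the gap between leavers and completers raises the 7.3 to 14.1 and lowers the 0.351 to 0.315. Three missing of 33 matches the historical loss of 9.5%. Even with all three scoring 0 and the SD widened, the hyperope bound is 35.4 (limit 32) and the myope bound 42.3 (limit 40).

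**The case against.** The strongest reply is that nothing is likely to change. At the planned means and SDs, a hyperope completer mean of 40 or lower has probability of about 0.8%, and a near acuity mean of 0.13 or worse about 0.01%. At historical attrition neither CLUE test can tip within the 0–120 scale. That stands, and it limits the size of the point. It does depend on the planned means. Protocol section 1.5 reports one earlier hyperope study of these lenses with mean near acuity 0.173, beyond the 0.17 limit, although the present test averages over both strata.

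A reader might go further and infer that the check uses the primary model, duplicates the primary analysis and cannot show any effect of dropout. The documents do not support that. No imputation model is named. For CLUE, the primary set is completers, so imputing for dispensed leavers would use a different population, and their 3-day scores can move the mean by several points. Exact agreement follows only for acuity, or if the imputation is confined to the Per-Protocol set, where there is almost nothing to fill.

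Nor is it right that leavers' data are never taken. Protocol section 8.2 requires the current visit to be completed, so a subject stopped at Visit 2 has CLUE and Snellen acuity, and at Visit 3 both CLUE and logMAR precede the fit assessment. CLUE and logMAR are absent only for stops between scheduled visits, and logMAR for any stop before Visit 3. Finally, selective loss does not favour the lens on every endpoint. The two safety hypotheses use the Safety population and include unscheduled visits, so fit or slit-lamp failures seen before withdrawal count.

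**Conclusion.** The point holds as a gap in the sensitivity plan. The committed check is unspecified and by default assumes missing at random. It is uninformative for logMAR acuity if drawn from the primary model, and partly informative for CLUE only if run beyond the Per-Protocol set. The other check is discretionary and needs dropout above a level that no historical study exceeded. Nothing planned tests whether subjects who left for vision, comfort or fit were worse than their data predict.

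The consequence is modest. At the planned means the result should prove robust: hyperope CLUE with 10 missing tips at about 7 to 14. The check matters when a result lies near its limit: about 30 for a completer mean of 40 with 10 missing, and about 0.19 for near acuity of 0.13 with 20 missing. It would be wrong to conclude that the planned verdicts are unsafe.

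These figures assume the historical SDs, ignore site and covariate effects, and treat the missing scores as if they had been observed. Carrying the imputation uncertainty would bring the fixed-SD tipping values somewhat closer to the completer mean. The CLUE shifts rest on the assumed correlation and deficit.

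**What to change.** In SAP section 8.6, replace the imputation sentence with a specified analysis:

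1. State the imputation model and run it on all dispensed subjects, using the 3-day CLUE score where there is one.
2. Add a delta-adjusted tipping-point analysis. Shift imputed CLUE down in 5-point steps and imputed logMAR up in 0.05 steps until each credible bound crosses its limit, and report the tipping shift for each efficacy hypothesis.
3. Apply the shift separately to subjects who discontinued for vision, comfort or fit. These reasons are already recorded (SAP sections 10.1 and 12.4).

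Subjects who fail dispensing at Visit 1 fall outside this set, so report their number and reasons beside it. The cost is a short SAP change, some code and a little extra analysis, with no new data. Collecting CLUE and binocular logMAR from early leavers still wearing the lenses would strengthen the analysis. It should be optional, because it needs a protocol revision and ethics review, and the SAP is dated about three months after protocol version 4.0 for a study expected to last 2–3 months.
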